#### 9.4. Deaths, Serious Adverse Events, and Other Significant Adverse Events

A serious adverse event is an adverse event that fulfills the following criteria:

- Is fatal (results in death);
- Is life-threatening (Note: the term "life-threatening" refers to an event in which the patient was at risk of death at the time of the event; it does not refer to an event that could hypothetically have caused death had it been more severe);
- Requires inpatient hospitalization or prolongation of existing hospitalization (hospitalization is defined as an inpatient admission, regardless of length of stay);
- Results in persistent or significant disability/incapacity (a substantial disruption of the patient's ability to conduct normal life functions);
- Is a congenital anomaly/birth defect; or
- Constitutes an important medical event that may jeopardize the patient or may require medical or surgical intervention to prevent one of the other outcomes listed above.

Serious adverse events will be summarized according to Section 9.3.

By-patient listings will be provided for any deaths, serious adverse events, and adverse events leading to discontinuation of treatment. Treatment-emergent adverse events that result in dose interruption will also be identified.

#### 9.5. Clinical Laboratory Evaluation

Clinical laboratory samples should be collected at the beginning of each clinic visit and just prior to a dose on all Study Visit Days and will be processed by a central laboratory. In the event a patient is unable to attend an in-clinic visit due to COVID-19, clinical laboratory blood draws may be performed by a Home Health Care agency or a local laboratory.

Clinical laboratory variables will be presented in 4 ways. First, change from baseline to the minimum post-baseline value, maximum post-baseline value, and final value will be summarized. Baseline will be defined as the laboratory value obtained before the first dose of study drug on Day 1; if Day 1 values are unavailable, then values obtained at the Screening Visit will be used. Only post-baseline values on treatment will be eligible. The Follow-up Visit will be excluded from possible minimum, maximum, or final post-baseline values.

This analysis will be repeated with outlying values removed from eligibility for minimum and maximum values. An outlier is defined using the interquartile range (IQR). The IQR is equal to the third quartile minus the first quartile and will be calculated by visit and treatment group for each numeric parameter. The IQR will be multiplied by a constant of 1.5. Any value which is above 1.5 times IQR plus the third quartile or below 1.5 times IQR minus the first quartile will be considered an outlier and will be removed from eligibility for minimum, maximum, or final post-baseline values.

Second, shift tables will summarize by treatment group and active overall the number and percentage of patients with categorical changes from baseline defined by the laboratory normal reference range for each laboratory parameter (Below reference range, Within reference range, and Above reference range). The baseline category will be cross-tabulated with post-baseline category ( $3 \times 3$  table). The post baseline category will be assigned and summarized in 2 ways for each laboratory parameter: minimum post-baseline value and maximum post-baseline value. Only post-baseline values on treatment will be eligible. Patients will only be reported in the shift tables if they have both a baseline and post-baseline value.

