  - The SAP adds multiple imputation for the Modified Efficacy Population, which will include site 102. The primary multiple imputation for the Efficacy Population will not include site 102.

- Protocol Section 12.4.5.2 Tipping Point Analyses
  - The protocol states that "The patterns of interest for the tipping point analysis will consider two cases and will estimate tipping points for values where only missing values not at random (MNAR) are adjusted and also where all missing values are adjusted (i.e., two separate tipping point analyses)." The SAP specifies only one tipping point analysis due to the following:
    - This statement assumes that the primary imputation method would employ an MNAR assumption. It was determined that MAR would be reasonable upon blinded review of reasons for missing data, as prespecified in Protocol Section 12.4.4.
    - To test the MAR assumption, an additional sensitivity analysis employing an MNAR assumption was added.
    - The values that will be MNAR for the MNAR sensitivity analysis are study discontinuations due to TEAEs or lack of efficacy. These values will be imputed using the control arm. As such, adjusting these values would shift those patients to be worse than placebo. As placebo in this study is a true placebo, this is not a realistic or informative shift.
  - The protocol states, "Missing values will not be imputed for efficacy endpoints which are not derived from SALT scores." The SAP adds multiple imputation for the SPRO endpoints because SPRO at Week 24 is an alpha-controlled key secondary endpoint and the treatment of missing data should align with the treatment of missing data for the other alpha-controlled endpoints.
- Protocol Section 12.4.8 Safety
  - Adverse Events
    - The protocol states that "Proportions for adverse events that are gender-specific (e.g., dysmenorrhea) will be based on the number of patients from that gender." The SAP specifies that the proportion of adverse events will be based on the number of patients in the safety population, even gender-specific adverse events. This change is in line with previous studies in this program and generally accepted conventions.
  - Clinical Laboratory
    - Two additional presentations of labs were added to the SAP in light of outliers seen in blinded data review throughout the study (IQR) and to observe values over time (by visit summaries).
- Other changes:
  - Analyses for COVID-19 were added in Section 11 of the SAP.

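### SAP 9.5 repeats the laboratory change-to-minimum/maximum analysis after removing values by a within-arm 1.5 × IQR rule, which deletes genuine extremes confined to a minority of patients and is also misstated

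*SAP*

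**What the plan says.** SAP Section 9.5 first summarises, for each laboratory parameter, the change from baseline to each patient's lowest, highest and last on-treatment value. It then adds a second pass: "This analysis will be repeated with outlying values removed from eligibility for minimum and maximum values".

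The criterion is numerical only. The IQR "will be calculated by visit and treatment group for each numeric parameter". "The IQR will be multiplied by a constant of 1.5". A value is an outlier if it meets either of two conditions:

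- upper: "Any value which is above 1.5 times IQR plus the third quartile"
- lower: "below 1.5 times IQR minus the first quartile"

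Such values are "removed from eligibility for minimum, maximum, or final post-baseline values". Baseline is the pre-dose Day 1 result, or Screening if that is unavailable, and carries no outlier condition. The laboratory analyses cover chemistry, hematology and lipids. SAP Section 13 gives the only reason for the addition: outliers had been noticed during blinded data review.

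**The concern.** A change-to-maximum table exists to show each patient's most extreme result. This rule removes results because they are extreme, with no reference to sample quality, units, repeat testing or agreement with neighbouring visits. If a drug raises a parameter markedly in one patient in ten, those results lie far outside the middle half of their arm and are the ones removed.

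The limits are also computed separately by arm, so whether a given value counts depends on the spread of the arm it belongs to. A drug that widens the spread moves its own limit.

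What is at stake is interpretation. A reader who sees an arm difference shrink once outliers are removed will tend to conclude that it was artefact. This rule can produce that shrinkage when every elevation is real.

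**Working it through.** The plan states no figure for this rule, so there is nothing to reproduce. The multiplier and grouping come from SAP 9.5. The arm size of 110 (12 mg and placebo) comes from Protocol 12.1. The 7 on-treatment visits (Weeks 2, 4, 8, 12, 16, 20, 24) come from the schedule of assessments. Distributions and effect sizes are assumptions, because the documents give none.

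**1. The limits by hand (illustrative quartiles).** Upper limit = Q3 + 1.5 × (Q3 − Q1).

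- Placebo, quartiles 80/120: 120 + 1.5 × 40 = 180.
- Active, quartiles 90/160: 160 + 1.5 × 70 = 265.

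A value of 200 is dropped on placebo and kept on drug.

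**2. Error-free data are flagged too.** For normal data the limits lie at 0.6745 × 4 = 2.698 SD, so 0.7% of values are flagged. For lognormal data with SD of log 0.3, 0.5, 0.7 and 1.0, the upper limit alone flags 2.2%, 3.8%, 5.4% and 7.8%.

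**3. Intermittent rises.** Simulation: 110 per arm, 7 visits, 10% of drug patients with rises at about 30% of visits, 600 replicates, upper limit applied by arm and visit.

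| Between/within-patient SD of log | Rise | Drug-caused values deleted | Arm difference in mean change to maximum remaining |
|---|---|---|---|
| 0.30/0.25 | 2-fold | 42% | 43% |
| 0.30/0.25 | 3-fold | 77% | 16% |
| 0.30/0.25 | 5-fold | 98% | 2% |
| 0.40/0.35 | 2-fold | 31% | 52% |
| 0.40/0.35 | 3-fold | 58% | 28% |
| 0.40/0.35 | 5-fold | 88% | 8% |

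In the 3-fold, narrower case the difference falls from 0.222 to 0.036, and 0.036/0.222 = 16%. About 3–4% of ordinary placebo values are deleted as well. Repeat runs agree within a few percentage points.

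**4. Persistent or common effects.** In the narrower-spread model, a 3-fold rise at every visit in 10%, 20% and 30% of patients leaves about 37%, 57% and 77–79% of the difference. With 30% affected, 21% of drug-caused values are deleted. A 20% upward shift of the whole arm leaves 94%.

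**5. A second model.** Median 100, SD of log 0.5, within-patient correlation 0.6, persistent 4-fold rise, 400 runs. The mean placebo upper limit is 242. The placebo mean change to maximum is 55.3 untrimmed and 40.4 trimmed.

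| Active patients affected | Mean upper limit, active | Affected patients' values deleted | Arm difference, untrimmed | Arm difference, trimmed |
|---|---|---|---|---|
| 5% | 265 | 80% | 83.5 − 55.3 = 28.2 | 47.5 − 40.4 = 7.1 |
| 10% | 288 | 74% | 105.1 − 55.3 = 49.8 | 55.2 − 40.4 = 14.8 |
| 20% | 378 | 55% | 156.2 − 55.3 = 100.9 | 84.1 − 40.4 = 43.7 |
| 30% | 551 | 26% | 207.1 − 55.3 = 151.8 | 142.5 − 40.4 = 102.1 |

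With 10% affected, about 4% of active patients (0.04 × 110 ≈ 4) have no eligible value left, so they drop out of the trimmed table.

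**6. The lower limit as written.** Read literally it is 1.5 × IQR − Q1; the usual limit is Q1 − 1.5 × IQR. One is the negative of the other.

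- Quartiles 80/120: literal 60 − 80 = −20; usual 80 − 60 = 20. No positive value can fall below −20, so no low value is removed.
- The literal limit is positive only when 1.5 × (Q3 − Q1) > Q1, that is, when Q3 > (5/3) × Q1. For a lognormal parameter with SD of log 0.7 it is 0.846 of the median and would remove about 41% of values.

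Reversing the terms does not settle the matter. For an assumed platelet-like parameter (mean 260, SD 60) the usual limit is about 98. Results below the platelet threshold of 75 in Protocol Table 3 would then be removed.

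**7. Final values.** The sentence introducing the repeat confines removal to minimum and maximum, while the closing sentence adds the final value. Under the second reading, a patient whose last result is flagged has an earlier visit reported as final.

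**The case against.** The strongest reply is that little depends on this table. It is an added repeat, disclosed in SAP Section 13 and prompted by blinded review. The untrimmed version stays beside it. Shift tables on minimum and maximum values carry no outlier rule, and Section 9.5 keeps Grade 3/4 treatment-emergent counts, by-visit means, listings, and box plots with dose-interruption limits. Clinically significant abnormalities are also reported as adverse events (Protocol 10.13 and 12.4.8). Safety summaries are descriptive, without tests (SAP 9.1). All of this stands and limits the severity, but it does not make the repeat valid.

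Three stronger readings are tempting and are not supported:

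- *The trimmed table will look reassuring whether or not the drug causes elevations.* Persistent or common effects largely survive (steps 4 and 5). The severe losses belong to rare, intermittent rises.
- *Arm-specific limits systematically favour the drug.* In the hand example the placebo value is dropped and the drug value kept, which makes the drug look worse. Which arm gains depends on which has the wider quartiles.
- *Leaving outlying baselines in biases the comparison.* Baseline precedes dosing in randomised arms, so this mainly adds noise. In the second model about 4% of baselines lie above their own upper limit. It is an inconsistency of lesser weight.

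Two points on the remedy are also fair. The median is already a default statistic (SAP Section 4), so only quartiles would be new. Data cleaning before lock (Protocol 14.5) should already catch many errors.

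**Conclusion.** The concern holds as a defect in one supplementary safety table. Followed as written, the rule cannot separate error from toxicity, and it removes many genuine extremes when they occur in a minority of patients. For intermittent 2- to 5-fold rises in 10% of patients, about 40–98% of those values are deleted and about 2–43% of the arm difference remains (narrower assumed spread). With wider spread the figures are 31–88% and 8–52%. For persistent 3-fold rises in 10–30% of patients, about 37–79% remains. The sizes rest on assumed lognormal data and assumed effect patterns. The deletion of minority extremes follows from the rule itself.

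The arm-dependence of the limit and the two drafting faults (final values, reversed lower limit) need no distributional assumption. A reader might infer that safety data are lost or that the plan hides toxicity. The documents do not support that, because every result remains in untrimmed outputs. The change should be made, but it does not threaten the trial's conclusions.

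**What to change.** In SAP Section 9.5, replace the IQR rule. The repeat should exclude only values documented before unblinding as sample, unit or laboratory errors, using one list for all arms applied to baseline and post-baseline values alike. Final values should not be removed because of spread. To reduce the influence of extremes without deleting them, add quartiles to the median already planned for the untrimmed change to minimum and maximum. The reversed lower limit and the disagreement over final values then disappear with the rule; Section 13 should be updated to match.

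The cost is SAP wording and a blinded list of erroneous results. The automatically trimmed table is lost, and the repeat may come out close to the main table. No study procedure or patient management changes.

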# 9.6. Vital Signs, Physical Findings, and Other Observations Related to Safety

#### 9.6.1. Vital Signs

Vital signs will be measured after the patient has been in a supine or semi-supine position for at least 5 minutes and will include blood pressure, pulse rate, respiratory rate, and temperature.

Height will only be measured at the Screening Visit. Weight and vital signs will be measured according to the Schedule of Assessments (Appendix 15.2). Weight and height will be used to calculate the patient's body mass index at Screening.

The mean and mean change from baseline to each scheduled assessment will be summarized descriptively by treatment group and overall for each vital sign variable specified in the protocol.

Baseline will be defined as the last vital sign value obtained before the first dose of study drug on Day 1; if Day 1 values are unavailable, then values obtained at the Screening Visit will be used.

The number and percentage of patients with at least 1 PCS vital sign value, defined as for laboratory values in Section 9.5, will be summarized descriptively by treatment group and overall. A listing of vital signs by patient will also be provided.

#### 9.6.2. Physical Examinations

A complete physical examination will consist of an examination of all major organ systems to include, but not be limited to, chest auscultation, abdominal auscultation and palpation, head, eyes, ears, nose and throat. An assessment for active signs and symptoms of infection including tuberculosis, and skin examinations for non-melanoma skin cancers, will be performed. Evaluation for progressive multifocal leukoencephalopathy symptoms such as facial droop, general weakness, clumsiness, trouble speaking, personality changes, memory problems, and vision changes will be assessed.

Additionally, an assessment for the presence or absence of nasal hair will be performed during complete physical exams. Complete physical exams will be performed at screening, baseline, Week 24, and Week 28. The presence or absence of nasal hair will be summarized as counts and percentages by treatment group at baseline and Week 24 for the Safety Population.

Brief physical examinations will include assessment for active signs and symptoms of infection, including tuberculosis, skin examinations for non-melanoma skin, and an evaluation for PML

symptoms such as facial droop, general weakness, clumsiness, trouble speaking, personality changes, memory problems, and vision changes. Physical examinations will be performed according to the Schedule of Events (Appendix 15.2).

A listing of the date and type of physical examinations performed will be provided. The listing will include presence or absence of nasal hair. Deteriorations from baseline on physical examination will be coded as adverse events and summarized as such.

#### 9.6.3. Other Safety Measures

#### 9.6.3.1. 12-Lead Electrocardiogram

Twelve-lead electrocardiograms (ECG) will be performed at the screening visit, Week 12, and end of study after the patient has rested in a supine or semi-supine position for at least 5 minutes. Individual parameters including heart rate, PR, QT, QTcF (Frederica's correction), QRS, RR intervals will be collected. If a patient is unable to attend an in-person clinic visit due to COVID-19, an ECG may not be performed. Missed assessments will be recorded in the eCRF as due to COVID-19.

The mean and mean change from baseline to each scheduled assessment will be summarized descriptively by treatment group and overall for each ECG variable specified in the protocol.

A listing of ECG results will be provided. A listing of abnormal ECG findings will also be provided.

# **10. PHARMACOKINETIC EVALUATION**

Sparse PK sampling was performed in this study in order to contribute to a cross study population PK analysis. Covariates from this study and others will include age, gender, race, weight (or BMI), for the population PK analysis of CTP-543. Exposure-response relationships for both efficacy and safety parameters will also be assessed. This population PK analysis will be described in a separate analysis plan and a separate population PK report will be generated. The data will not be summarized in the CP543.3002 final clinical study report.

A by-patient listing of whether PK sampling was performed will be included in the final clinical study report.

# 11. OTHER ANALYSES

In light of the COVID-19 pandemic and recommendations in the FDA guidance document "Statistical Considerations for Clinical Trials During the COVID-19 Public Health Emergency", the following additional listings and summaries will be provided:

- Listing of patients affected by COVID-19 related study disruption, defined as missed or remote visits or assessments indicated per the eCRF.
- Listing of dosing exceptions related to COVID-19.
- Summary and listing of protocol deviations related to COVID-19, per Section 7.1.
- Summary of TEAEs related to COVID-19 by system organ class and preferred term and TEAEs related to COVID-19 leading to study drug discontinuation by system organ class and preferred term, per Section 9.3. Relationship to COVID-19 will be determined using the Standard MedDRA Query for COVID-19 (Appendix 15.4) and may also include preferred terms related to vaccinations if the collected term indicates relation to COVID-19 (ex: Vaccination complication, Vaccination site pain). Terms may be reviewed by the sponsor prior to database lock to finalize the list of preferred terms.
- Listing of TEAEs related to COVID-19.
- Listing of prior and concomitant medications related to COVID-19, where relationship to COVID-19 is defined by the question "Related to COVID-19?" on the Prior and Concomitant Medications CRF page.
- Summary of number and percentage of randomized subjects with missed visits due to COVID-19.

# 12. INTERIM ANALYSES AND DATA MONITORING

An independent data monitoring committee (DMC) will perform regular safety assessments based on a review of cumulative safety data. The DMC may advise study and/or treatment arm cessation due to intolerability at any time. There are no plans to perform interim efficacy analyses or to discontinue the study early due to demonstration of efficacy differences. Therefore, no adjustment of Type I error is required for interim analyses.

#### **13.** CHANGES TO THE ANALYSES PLANNED IN THE PROTOCOL

The following changes to the protocol were made:

- Protocol Section 12.3.1 Analysis Populations
  - The Modified Efficacy Population was added as an analysis population. The Modified Efficacy Population is defined as the protocol defines the Efficacy Population. The SAP updates the definition of the Efficacy Population to exclude site 102 due to repeated and persistent non-compliance with the study procedures.
  - The text "In the event patients incorrectly receive treatment associated with a different treatment group, they will be analyzed "as randomized" for efficacy and "as treated" for safety" was amended to add additional information in the event that a patient is given only a portion of the incorrect treatment.
- Protocol Section 12.4.1 Disposition and Baseline Characteristics
  - This section of the protocol does not distinguish treatment discontinuation from study discontinuation. The SAP adds detail and specifies that both treatment and study discontinuation, as well as reasons for discontinuation for both treatment and study will be summarized in line with FDA feedback and the eCRF.
- Protocol Section 12.4.2
  - Primary Efficacy Endpoint
    - The protocol uses the general umbrella term "Cochran-Mantel-Haenszel test" to describe the primary analysis. The SAP specifies "Mantel-Haenszel common risk difference" in reference to analyses which use multiple imputation. This is in line with Protocol Section 12.4.5.1. Analysis of Imputed Datasets and was done to avoid confusion with stratified CMH tests utilized for non-imputed data.
  - Other Efficacy Endpoints
    - The protocol specifies that analyses of HADS will use an MMRM. The SAP updates this analysis to use an ANCOVA as the questionnaire was only collected at one post-baseline visit.
- Protocol Section 12.4.5 Multiple Imputation
  - The protocol states, "Missing values will be imputed with a sequential regression approach under the assumption of multivariate normality." The SAP removes the phrase "under the assumption of multivariate normality" as it is not necessarily applicable when using the FCS method.
  - The protocol states that the discriminant function will be used for classification variables. The logistic function was specified for SPRO imputation because it is ordinal rather than nominal.
  - The SAP adds multiple imputation for the Modified Efficacy Population, which will include site 102. The primary multiple imputation for the Efficacy Population will not include site 102.

- Protocol Section 12.4.5.2 Tipping Point Analyses
  - The protocol states that "The patterns of interest for the tipping point analysis will consider two cases and will estimate tipping points for values where only missing values not at random (MNAR) are adjusted and also where all missing values are adjusted (i.e., two separate tipping point analyses)." The SAP specifies only one tipping point analysis due to the following:
    - This statement assumes that the primary imputation method would employ an MNAR assumption. It was determined that MAR would be reasonable upon blinded review of reasons for missing data, as prespecified in Protocol Section 12.4.4.
    - To test the MAR assumption, an additional sensitivity analysis employing an MNAR assumption was added.
    - The values that will be MNAR for the MNAR sensitivity analysis are study discontinuations due to TEAEs or lack of efficacy. These values will be imputed using the control arm. As such, adjusting these values would shift those patients to be worse than placebo. As placebo in this study is a true placebo, this is not a realistic or informative shift.
  - The protocol states, "Missing values will not be imputed for efficacy endpoints which are not derived from SALT scores." The SAP adds multiple imputation for the SPRO endpoints because SPRO at Week 24 is an alpha-controlled key secondary endpoint and the treatment of missing data should align with the treatment of missing data for the other alpha-controlled endpoints.
- Protocol Section 12.4.8 Safety
  - Adverse Events
    - The protocol states that "Proportions for adverse events that are gender-specific (e.g., dysmenorrhea) will be based on the number of patients from that gender." The SAP specifies that the proportion of adverse events will be based on the number of patients in the safety population, even gender-specific adverse events. This change is in line with previous studies in this program and generally accepted conventions.
  - Clinical Laboratory
    - Two additional presentations of labs were added to the SAP in light of outliers seen in blinded data review throughout the study (IQR) and to observe values over time (by visit summaries).
- Other changes:
  - Analyses for COVID-19 were added in Section 11 of the SAP.
  - Log-rank statistics related to the primary endpoint were added as an Other Efficacy Endpoint. This analysis is descriptive only.

